## **Participants**

Ethical approval was provided by the School of Life Sciences ethics committee at the University of Hull which was in accordance with the 1964 Helsinki declaration and its later amendments or comparable ethical standards. A total of 42 apparently healthy men and women between the age of 18-65 years were recruited to the study. Participant characteristics are given in Table 1. Enrolled individuals reported no medical history of cardiometabolic or limiting respiratory disease, were non-smokers, had a body mass index  $<30 \text{ kg m}^{-2}$ , classified as recreationally active [25] and none were taking any medication that would affect heart rate. As a condition of enrolment, those over 45 years obtained written medical clearance from a general practitioner and underwent resting and exercise 12-lead electrocardiogram (ECG) (GE Healthcare, Chalfont St Giles, United Kingdom). Written informed consent and a pre-exercise medical questionnaire was completed by all.

\*\*\*Table 1 here\*\*\*

## **Cardiopulmonary Exercise Testing**

Maximal CPETs were conducted in accordance with the American Thoracic Society (ATS) and the American College of Chest Physicians (ACCP) guidelines [26]. An Oxycon pro (Jaeger, Hoechburg, Germany) breath by breath metabolic cart was used to collect respiratory gas exchange data. Automatic and manual calibration evaluated ambient temperature, humidity, barometric pressure and altitude. Calibration of the air flow volume was conducted using a 3L syringe and by automatic calibration. Two-point gas calibration was also conducted to ensure accurate measures of inspired

O2 and expired CO2 [27]. Tests were performed on a GE e-bike ergometer (GE Healthcare, Buckinghamshire, UK) using a ramp protocol [26]. The protocol consisted of a three-minute rest phase, three minutes of unloaded cycling, followed by a personalised ramp test [28] (ramp rate ranged between 15 and 30 watts) with work rate continually increased every one to three seconds. Participants performed the same ramp rate pre and post testing. Participants were asked to pedal at a cadence of 70 rpm until they reached volitional exhaustion at a protocol duration between eight to twelve minutes. Self-reported rating of perceived exertion (RPE) scores using the 6-20 scale [29] and heart rate (HR) (FT1 heart rate monitor, Polar Electro, OY, Finland) was recorded during the last five seconds of each minute of the test, at maximum exercise and during the recovery period. Together with verbal encouragement to volitional exhaustion,  $\dot{V}O_{2max}$  was attained by participants achieving at least two of the following criteria:  $\dot{V}O_2$  plateau as determined by a failure of  $\dot{V}O_2$  increase by 150 ml/min with further increases in workload analysed by breath by breath gas exchange data averaged over 15 seconds [30], respiratory exchange ratio (RER) > 1.10, achieve > 85% age predicated HRmax and a RPE > 17 on the 6-20 Borg scale [27].  $\dot{V}O_2$  at VAT was defined using the 'V slope' method [31] and verified using ventilatory equivalents. Peak power output (PPO) (watts) and HRmax were defined as the highest value achieved during the CPET with maximum  $\dot{V}O_2/HR$  determined by the ratio of  $\dot{V}O_{2max}$  and HRmax.

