### **Statistical Analysis**

Statistical analysis was conducted using SPSS version 24 (IBM, New York, USA). An independent t-test was used to identify group differences at baseline. Assumptions of normality were verified using the Shapiro-Wilk test. Skewness and kurtosis of distribution was visually examined. Non-normally

distributed data was presented as median and interquartile range (IQR). A two-way (condition x time) repeated measures analysis of variance (ANOVA) was used to compare CRF pre-and post-training. Post-hoc analysis for the main effects and interactions was assessed using a Bonferroni adjustment. Group differences were compared using independent t tests. Variables were displayed as mean with 95% confidence intervals (95% CI) or standard deviation ( $\pm$ ) where specified. Partial eta squared ( $\eta_p^2$ ) effect sizes were also calculated with 0.01, 0.06 and 0.14 representing small, medium and large effect sizes, respectively [35].

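### Does a fixed 150 ml/min plateau cut-off with no stated comparison lag undermine the VO2max result?

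*Combined protocol and SAP*

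**What the plan says.** Study Design makes VO2max, from a maximal cycle test before and after eight weeks of training, the measure of effectiveness. Cardiopulmonary Exercise Testing says that VO2max "was attained by participants achieving at least two of the following criteria". The four criteria are a VO2 plateau, a respiratory exchange ratio above 1.10, a heart rate above 85% of the age-predicted maximum, and perceived exertion above 17 on the 6-20 scale. The plateau is counted when VO2 fails to "increase by 150 ml/min with further increases in workload analysed by breath by breath gas exchange data averaged over 15 seconds", and the rule carries a citation (reference 30).

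The same section says that the "ramp rate ranged between 15 and 30 watts", without a time unit, "with work rate continually increased every one to three seconds". It adds: "Participants performed the same ramp rate pre and post testing". Participants cycled to volitional exhaustion with verbal encouragement.

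In Statistical Analysis, a condition-by-time repeated measures analysis of variance "was used to compare CRF pre-and post-training". That section refers to neither the plateau nor the other three criteria, and gives no rule for a test that does not meet them.

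**The concern.** A rise of less than 150 ml/min is informative only if normal exercise would have produced a clearly larger rise over the same step in workload. On a staged test the stage defines that step. Here the work rate climbs almost continuously, so nothing in the text fixes the step, and the only interval printed is the 15-s averaging window. If that window is also taken as the gap between compared values, the workload hardly changes between them and almost any pair passes. Requiring two criteria of four would then come close to requiring one of the other three.

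The cut-off is also the same for a 15 W and a 30 W ramp, so the check is easier to pass on a slow ramp. At stake is the assurance that the values entering the main comparison are true maxima. The heart-rate maximum from the same test also sets training intensity in both arms and is the denominator for fidelity.

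**Working it through.** The plan gives no computed figure for the plateau rule, so there is nothing of its own to reproduce.

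**Inputs from the plan:** cut-off 150 ml/min; 15-s averages; ramp 15 to 30 W; test duration eight to twelve minutes.

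**Assumptions, not in the plan:**
- The ramp is per minute. If the stated duration is the ramp phase, this gives end workloads of 15 x 8 = 120 W to 15 x 12 = 180 W, and 30 x 8 = 240 W to 30 x 12 = 360 W.
- Oxygen cost is 8-12 ml/min per W.
- Noise in each 15-s average is independent, with SD 30-100 ml/min.

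**Step 1. Expected submaximal rise** = ramp x (gap/60) x oxygen cost. For example, adjacent averages at 15 W/min give 15 x 15/60 = 3.75 W, hence 3.75 x 8 = 30 to 3.75 x 12 = 45 ml/min.

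**Step 2. Chance that one purely submaximal comparison falls below 150** = Phi((150 - rise)/(SD x sqrt 2)). The lowest value at a 15-s gap and 30 W/min is Phi((150 - 90)/(100 x 1.414)) = Phi(0.424) = 0.664. The highest at 15 W/min is Phi((150 - 30)/(30 x 1.414)) = Phi(2.83) = 0.998.

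| Gap | Rise, 15 W/min | Chance | Rise, 30 W/min | Chance |
|---|---|---|---|---|
| 15 s | 30-45 | 0.771-0.998 | 60-90 | 0.664-0.983 |
| 30 s | 60-90 | 0.664-0.983 | 120-180 | 0.240-0.760 |
| 60 s | 120-180 | 0.240-0.760 | 240-360 | 0.000-0.262 |

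For adjacent averages to rise by 150 ml/min, the oxygen cost would have to be 150/3.75 = 40 ml/min per W at 15 W/min, or 150/7.5 = 20 at 30 W/min. Both lie well outside the assumed range.

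**Step 3. Gap at which the submaximal rise equals 150** = 150 x 60/(ramp x oxygen cost). At 15 W/min: 9000/(15 x 12) = 50 s to 9000/(15 x 8) = 75 s. At 30 W/min: 9000/(30 x 12) = 25 s to 9000/(30 x 8) = 37.5 s. The two ranges do not overlap, so no single gap makes the cut-off equally strict across ramps.

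**Step 4. When a false plateau changes the label.** Count how many of the other three criteria a test meets:
- none: plateau plus none is one, and the test still fails;
- one: the false plateau makes two, and the label changes;
- two or three: the test passes without the plateau.

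So the chances in Step 2 are not chances of wrongly certifying a test. They matter only for tests meeting exactly one other criterion, and the plan gives no basis for estimating how many those are.

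**Step 5. Does the label reach the result?** The repeated measures analysis takes the CRF values before and after training, and plateau status is not an input. Peak power and maximum heart rate are defined as the highest values reached in the test, whatever the criteria show, so training targets, the fidelity denominator and the heart-rate term of maximum VO2/HR do not depend on the plateau rule. Ramp rate is constant within a participant, so the uneven strictness does not differ between that participant's two visits. If tests failing the criteria had been left out, which the plan does not say, a lenient plateau would leave out fewer participants, not more.

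**The case for a change.** The strongest case for a change has three parts. First, the uneven strictness in Step 3 holds for any single gap, so it does not rely on the adjacent-average reading. Second, if the plateau is nearly automatic, a heart rate just above 85% of the age-predicted maximum could certify a test alone. Training Interventions sets HIIT intervals above 85% of measured maximum; the reference maximum differs, but this shows that such a level is not in itself a maximum. Third, the VO2max value is not expressly defined as the highest averaged VO2, although peak power and heart rate are defined that way, and failed tests have no stated handling. A repair would need only text and reprocessing of recorded data.

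The arithmetic stands, and so does the point that the gap is not restated. The rest carries less weight. Fifteen seconds is given as a smoothing window, not as a comparison gap. Heart rate and exertion are recorded each minute, so a one-minute comparison is at least as natural, and the cited reference, not available here, may fix it. The plateau is not the sole safeguard: three other criteria and cycling to exhaustion remain.

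The possible repairs gain little. A cut-off scaled to ramp rate needs a fraction that nothing in the plan supplies, and it would alter only the label. Dropping the plateau and requiring two of the other three is a trade-off that has not been shown to verify maximal effort better. Taking the highest averaged VO2 of every tested participant is the ordinary reading, and an analyst would adopt it without being told. Counts of tests meeting each criterion would be useful in a report, but they would not change the comparison.

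**Conclusion.** The observation is right and its consequence is small. On adjacent 15-s averages the plateau criterion would be met in 66% to 99.8% of purely submaximal comparisons. At a 60-s gap this falls to 24-76% on a 15 W/min ramp and 0-26% on a 30 W/min ramp. These figures rest on a per-minute ramp, an oxygen cost of 8-12 ml/min per W and an independent noise SD of 30-100 ml/min, none of which the plan states.

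The effect is confined to how firmly a test is confirmed as maximal, and only for tests that meet exactly one of the other three criteria. The measured VO2 is unchanged, and no bias between HIIT and CT is shown. The planned analysis would give the same estimate and conclusion under a stricter or scaled rule, provided that every available test is analysed, which is the natural reading. The unstated gap is a missing detail to settle when the breath-by-breath data are processed and to report with the results. The plan needs no change on this point.

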### **Training Interventions**

The HIIT group were asked to perform ten one-minute HIIT intervals, each followed by one minute of active recovery (AR) (total exercise time 20 minutes). Resulting from the CPET, HIIT was set at > 85% HRmax with a specific HR designated for this criterion. Active recovery was set at a load corresponding to 25-50 watts. Sessions were performed on a Wattbike trainer (Wattbike Ltd, Nottingham, UK). The CT group completed a practical seven-station mixed modality exercise circuit (cycle ergometer, rower, treadmill, sit to stand/squats, knee to elbow and leg kickback with bicep curl) at an intensity

of 60-80%  $HR_{max}$  (calculated from CPET). No resistance equipment was involved, only body weight. Participants initially performed 20 minutes of CT with duration increased by five minutes per week until the desired 40 minutes. Each station was occupied for three to six minutes depending on session duration, moving from one station to the next with minimal rest. During both interventions, HR was measured in last 5 seconds of each station/interval using a FT1 polar heart rate monitor (Polar Electro, OY, Finland) with each CT session timed using a stop watch (Axprod S.L, Guipuzcoa, Spain). Intensity for both interventions was adjusted throughout by the investigator to ensure an appropriate HR range and successful completion of the protocol. Participants were made aware of their HR ranges and verbal encouragement was given by the physiologist to help achieve and maintain these thresholds. Energy expenditure between HIIT and CT was not matched.

To assess the validity of the exercise interventions, participant fidelity to the desired exercise intensity was determined using cut points of  $>85\% HR_{max}$  and 60-80%  $HR_{max}$  for HIIT and CT respectively and reported using previous examples [32,33]. These values were calculated using the participants mean heart rate for each individual interval or station over the 16 sessions and was expressed as a percentage of  $HR_{max}$  as determined by CPET at visit 1. Specific fidelity thresholds were consulted to determine low ( $<50\%$ ), moderate (50-70%) and high ( $>70\%$ ) compliance [34]. Adherence was determined as a percentage of completed sessions, with 14 ( $> 85\%$ ) being the threshold for completion.

### **Statistical Analysis**

Statistical analysis was conducted using SPSS version 24 (IBM, New York, USA). An independent t-test was used to identify group differences at baseline. Assumptions of normality were verified using the Shapiro-Wilk test. Skewness and kurtosis of distribution was visually examined. Non-normally

distributed data was presented as median and interquartile range (IQR). A two-way (condition x time) repeated measures analysis of variance (ANOVA) was used to compare CRF pre-and post-training. Post-hoc analysis for the main effects and interactions was assessed using a Bonferroni adjustment. Group differences were compared using independent t tests. Variables were displayed as mean with 95% confidence intervals (95% CI) or standard deviation ( $\pm$ ) where specified. Partial eta squared ( $\eta_p^2$ ) effect sizes were also calculated with 0.01, 0.06 and 0.14 representing small, medium and large effect sizes, respectively [35].

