### **Study Design**

Participants were enrolled in a randomised control trial at the University of Hull to either eight weeks of HIIT or CT (two supervised sessions per week, accompanied by an exercise physiologist). A sample size of 38 using G\*Power 3.1 software was calculated based on previously published data in which the mean difference between HIIT and MICT was  $3.2 \text{ ml}\cdot\text{kg}^{-1}\cdot\text{min}^{-1}$  with a pooled standard deviation of  $3 \text{ ml}\cdot\text{kg}^{-1}\cdot\text{min}^{-1}$  [19]. Statistical significance was set at  $\alpha = 0.05$  and power set to 0.95. To allow for 10% attrition 42 individuals were recruited to the study. To assess the effectiveness of the interventions as determined by  $\dot{V}O_{2max}$ , a maximal cardiopulmonary exercise test (CPET) to volitional exhaustion on an electronically braked cycle ergometer at baseline (visit one), and following an eight-week exercise intervention of HIIT or CT (visit two) was conducted. When attending the assessments participants were asked not to take part in any strenuous exercise 24 hours prior to the appointment, to wear suitable comfortable clothing and avoid a large meal. Visit two CPET was performed within six days of completing the exercise interventions. A thorough warm-up and cool down before and after each exercise session. All were asked to maintain their habitual physical activity patterns during the intervention. Body mass index (BMI) was calculated by dividing body weight [23] by height in meters squared and was presented as  $\text{kg}\cdot\text{m}^{-2}$ . Resting blood pressure was measured after 15 minutes of rest using a sphygmomanometer (A.C. Cossor & Son Ltd, London UK)

and stethoscope (3M Healthcare, St Paul, MN). To provide a comprehensive account of the study the Consensus on Exercise Reporting Template (CERT) was consulted [24].

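### The condition x time ANOVA fixes the baseline VO2max coefficient at 1; ANCOVA on the measured baseline is usually more precise and, named as the main analysis, would settle which group comparison is meant

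*Combined protocol and SAP*

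**What the plan says.** VO2max is the outcome by which the two programmes are judged, and the Study Design section has it measured by a maximal exercise test twice: "at baseline (visit one), and following an eight-week exercise intervention of HIIT or CT (visit two) was conducted".

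The Statistical Analysis section then lists several between-group analyses:

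- The main model: "A two-way (condition x time) repeated measures analysis of variance (ANOVA) was used to compare CRF pre-and post-training".
- Follow-up tests: "Post-hoc analysis for the main effects and interactions was assessed using a Bonferroni adjustment".
- A further comparison, with no variable named: "Group differences were compared using independent t tests".
- A baseline test: "An independent t-test was used to identify group differences at baseline".

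No model uses the visit-one value as a covariate, and no single contrast is named as the test of HIIT against CT. The sample size in the Study Design section is "based on previously published data in which the mean difference between HIIT and MICT was" 3.2 ml/kg/min, "with a pooled standard deviation of" 3 ml/kg/min. It is not said whether that SD refers to change or to values at one visit.

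**The concern.** With two arms and two visits, the term that compares training effects is the interaction, and it is the same test as a t-test on change. It subtracts the whole baseline value whatever the data say about how strongly visit two follows visit one. ANCOVA estimates that slope. In a randomised trial both are unbiased, so what is at stake is precision: a wider interval than necessary for the HIIT-CT difference in a small trial whose baseline values are measured by design.

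The second issue is which comparison is meant. The interaction, the condition main effect and a t-test on an unnamed variable are all on the list, and they estimate different things with very different power. The baseline significance test does not fill the gap: no action is described as following from it, and under randomisation it can only detect chance.

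**Working it through.** **Inputs.** From Study Design: difference 3.2, SD 3, alpha 0.05, power 0.95, N = 38 (42 with attrition), two visits. Assumed, because the documents are silent: 1:1 allocation (19 per arm), a two-sided test, equal SDs at the two visits, and a pre-post correlation ρ of 0.5 to 0.95.

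**1. The plan's own figure.** d = 3.2/3 = 1.067. One-sided, the normal approximation is 2 × (1.645 + 1.645)² / 1.067² = 19.02 per arm, which is 38 in total if rounded down. The noncentral t gives 40 (or 38 if d is rounded to 1.1). Two-sided, the noncentral t gives 48. So 38 is reached only as a one-sided calculation. Two-sided power with 19 per arm is 0.892, which is why the figures below start there and not at 0.95. That gap is a separate matter and is not caused by the ANOVA.

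**2. Interaction = change-score t-test.** In a simulated trial with 19 per arm, the interaction F and the squared t for change were both 4.4236.

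**3. Variances.** In units of the one-visit variance, change has variance 2(1 − ρ) and the ANCOVA residual has 1 − ρ². Their ratio is (1 + ρ)/2. Estimating the slope multiplies the ANCOVA variance by 1 + 1/(38 − 4) = 35/34 on average. At ρ = 0.8: 0.90 × 35/34 = 0.926. Break-even: ρ = 2 × 34/35 − 1 = 0.943.

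**4. Results if SD 3 is the SD of change.** The implied one-visit SD is 3/√(2(1 − ρ)).

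| ρ | ANCOVA/change variance | Power, change | Power, ANCOVA | Mean 95% CI width, change → ANCOVA | Power, t-test on visit two only |
|---|---|---|---|---|---|
| 0.5 | 0.772 | 0.892 | 0.953 | 3.92 → 3.44 | 0.892 |
| 0.7 | 0.875 | 0.892 | 0.927 | 3.92 → 3.67 | 0.698 |
| 0.8 | 0.926 | 0.892 | 0.913 | 3.92 → 3.78 | 0.525 |
| 0.9 | 0.978 | 0.892 | 0.898 | 3.92 → 3.88 | 0.299 |
| 0.95 | 1.004 | 0.892 | 0.891 | – | – |

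Simulation (60,000 trials per setting) gave variance ratios of 0.778, 0.873, 0.927 and 0.977 at ρ 0.5, 0.7, 0.8 and 0.9. Type I error was 0.049–0.051 for both methods, and the mean error of both estimators was within 0.01.

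**5. Chance imbalance.** Given a baseline difference Δ, the change-score estimate shifts by −(1 − ρ)Δ. One standard error of Δ is the one-visit SD × √(2/19). At ρ = 0.8 that is 4.74 × 0.324 = 1.54, so the shift is 0.2 × 1.54 = 0.31 ml/kg/min. At ρ = 0.7 and 0.9 the shift is 0.38 and 0.22. The standard error of the change-score difference is 3 × 0.324 = 0.97. This shift is the same loss as in step 3 seen conditionally, not a second one, and the planned confidence interval already covers it.

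**6. Results if SD 3 is the one-visit SD.** The variance ratios are unchanged. Change-score power is then 0.985 at ρ = 0.7 and 0.999 at 0.8, so from there up the gain is essentially in interval width: 3.03 to 2.84 at ρ = 0.7, and 1.75 to 1.74 at 0.9.

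**7. The listed contrasts differ.** In the simulated trial of step 2 (true difference 1.5), the condition main effect was 0.08, the visit-two difference 0.84, the interaction 1.53 and ANCOVA 1.38.

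**The case against.** The planned analysis contains no error. It is unbiased and holds its type I error, and the case for change is efficiency alone. That stands.

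The size of the gain rests on a correlation the documents do not give, and the design points to a high one: men and women aged 18–65, calibrated equipment and the same ramp rate at both visits. If SD 3 is the SD of change, ρ = 0.5 or 0.7 implies a one-visit SD of only 3.0 or 3.9, against 6.7 at ρ = 0.9. The smaller values look narrow for such a mixed group, though that is a judgement and not a documented figure. At ρ = 0.9 the gain is about 2% of variance. This too stands.

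The break-even and the shift formula need equal SDs. With s the ratio of visit-two to visit-one SD, the variance ratio is s²(1 − ρ²)(35/34) / (1 + s² − 2ρs). Break-even falls to about ρ = 0.87 at s = 1.05 and 0.81 at s = 1.10; with s = 1.10 and ρ = 0.9 the ratio is 0.2367/0.23 = 1.03. But the denominator equals s²(1 − ρ²) + (1 − ρs)², so the ratio can never exceed 35/34. The most ANCOVA can lose is about 3%.

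The t-test sentence may describe a follow-up to the ANOVA rather than a comparison of visit-two values, so those low powers show the cost of one possible reading, not of the plan. Naming the interaction as primary would also remove the ambiguity, without the gain in precision. Finally, the text is in the past tense, so the analysis may already have been run.

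**Conclusion.** The concern holds. The condition x time interaction is valid but fixes the baseline coefficient at 1. With 38 participants and equal SDs at the two visits, ANCOVA is more precise for any ρ below about 0.94: variance falls by about 23% at ρ = 0.5, 12% at 0.7, 7% at 0.8 and 2% at 0.9. If the SDs differ, the break-even moves, but the possible loss stays near 3%. ANCOVA brings two-sided power to the stated 0.95 only at about ρ = 0.5.

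The unclear between-group comparison matters most where the precision gain is smallest: a t-test on visit-two values alone would have power of about 0.30 at ρ = 0.9 if SD 3 is the SD of change. High repeatability therefore does not make the point moot. The change should be made, but the plan is not invalid without it. Confidence in the size is medium, because ρ and the meaning of SD 3 are not documented.

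**What to change.** - Make the main between-group analysis an ANCOVA of visit-two VO2max on arm, with visit-one VO2max as covariate. Report the adjusted mean difference with its 95% CI.
- Use the same model for VO2 at the ventilatory threshold and maximum VO2/HR, each with its own visit-one value.
- State that this replaces the unspecified independent t tests between groups.
- Replace the baseline significance test with a descriptive table by arm.
- If the results are already known, keep the planned analysis, report the ANCOVA beside it and label it post hoc. Say in either case which variable the t tests used.

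The cost is one residual degree of freedom (36 to 35) and about 3% variance inflation (1/34), both already counted in the figures above, plus revised SAP wording and one changed SPSS procedure. No new data are needed.

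### The HIIT versus CT comparison of VO2max does not adjust for baseline VO2max, and the plan does not say which of its tests decides it

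*Combined protocol and SAP*

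**What the plan says.** The last paragraph of the Design section gives one aim: to compare HIIT and CT on VO2max over eight weeks. Study Design confirms the outcome: the sentence beginning "To assess the effectiveness of the interventions as determined by" continues with VO2max, measured at visit one and again after training. The lead outcome is therefore clear.

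The Statistical Analysis section lists four things without ranking them:

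- a baseline comparison: "An independent t-test was used to identify group differences at baseline";
- the main model: "A two-way (condition x time) repeated measures analysis of variance (ANOVA) was used to compare CRF pre-and post-training";
- follow-up comparisons: "Post-hoc analysis for the main effects and interactions was assessed using a Bonferroni adjustment";
- a further sentence: "Group differences were compared using independent t tests".

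No sentence says which result answers the aim. No analysis uses baseline VO2max as a covariate. Study Design sets alpha at 0.05 and power at 0.95 for 38 participants, but does not name the test behind that calculation.

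**The concern.** There are two linked issues.

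**Baseline is collected but not used as a covariate.** The interaction compares changes, which amounts to fixing the slope on baseline at 1. A t test on post-training values fixes it at 0. A model with arm and baseline estimates the slope, and over much of the plausible range of correlation it gives a more precise comparison from the same data.

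**The deciding test is not labelled.** Baseline already has its own t-test sentence, so the second one seems to mean something more. It could mean:

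- (a) post-training values;
- (b) change scores;
- (c) follow-up of a significant interaction;
- (d) the fidelity and adherence measures described under Training Interventions.

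Under (a), the same VO2max data would be tested twice, with no rule for which result stands. The Bonferroni sentence concerns post-hoc analysis of ANOVA effects and does not clearly cover these t tests. The 0.05 in Study Design would then not be the error rate for the trial's question.

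**Working it through.** **Inputs.** From Study Design: difference 3.2 and SD 3 ml/kg/min, alpha 0.05, power 0.95, total 38. Assumed, because the documents do not give them: 1:1 allocation (19 per arm), two-sided testing, normal data with equal variances, and a pre-post correlation ρ of 0.5 to 0.9. The documents also do not say whether SD 3 is the SD of change or of a single measurement.

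**1. The plan's own figure.** Take SD 3 as the SD of the analysed variable.

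- Standardised difference: 3.2/3 = 1.067.
- Noncentrality at 19 per arm: 1.067 × √(19/2) = 3.29; critical t on 36 df = 2.028.
- Exact two-sided power: 0.892, not 0.95. Power of 0.95 needs 48 in total.
- A one-sided test needs 40 and has power 0.943 at 38.
- A repeated-measures group main effect with effect size f = d/2 and ρ = 0.5 gives exactly 38 (power 0.958). The plan does not state that variant, so the match shows only how 38 could have arisen.

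**2. The interaction and the change-score t test are one test.** With two arms and two time points, F for the interaction equals t² for change scores (checked on one simulated data set: both 0.1555). Reading (b) therefore adds no error.

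**3. Error under reading (a).** With no true difference, the correlation between the interaction statistic and the post-training t statistic is √((1−ρ)/2). The chance that at least one is significant is 0.05 + 0.05 − P(both).

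| ρ | Correlation of the tests | P(both) | P(either), normal theory | P(either), 200,000 simulated trials |
|---|---|---|---|---|
| 0.5 | 0.500 | 0.009 | 0.091 | 0.091 |
| 0.7 | 0.387 | 0.007 | 0.094 | 0.094 |
| 0.8 | 0.316 | 0.005 | 0.095 | 0.095 |
| 0.9 | 0.224 | 0.004 | 0.096 | 0.096 |

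The interaction alone gives 0.050. Under (c), the t test follows only a significant interaction, so the rate cannot exceed 0.05. Under (d), it is not a VO2max test at all.

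**4. What baseline adjustment gains.** Let σ be the single-measurement SD. The change variance is 2σ²(1−ρ) and the residual variance after adjustment is σ²(1−ρ²). Their ratio is (1+ρ)/2, so the residual SD is the change SD × √((1+ρ)/2). With change SD 3 and true difference 3.2, simulation gives:

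| ρ | Residual SD | Power, interaction | Power, adjusted | Mean 95% CI width, interaction | Mean 95% CI width, adjusted |
|---|---|---|---|---|---|
| 0.5 | 2.60 | 0.89 | 0.95 | 3.92 | 3.45 |
| 0.7 | 2.77 | 0.89 | 0.93 | 3.92 | 3.67 |
| 0.8 | 2.85 | 0.89 | 0.91 | 3.92 | 3.78 |
| 0.9 | 2.92 | 0.89 | 0.90 | 3.92 | 3.88 |
| 0.95 | 2.96 | 0.89 | 0.89 | 3.92 | 3.93 |

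At ρ = 0.95 the factor √((1+ρ)/2) is 0.987. That saving is used up by the lost degree of freedom (35 instead of 36) and by estimating the slope.

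If SD 3 is instead the single-measurement SD, power is 0.892, 0.985, 0.999 and 1.000 for the interaction and 0.954, 0.993, 0.999 and 1.000 adjusted, at ρ = 0.5, 0.7, 0.8 and 0.9. The power gain is then about 6 points at 0.5 and under 1 point from 0.7 upwards.

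**The case against.** The strongest reply is that the deciding test can be inferred. The aim concerns the effect of two programmes over eight weeks, VO2max is measured before and after, and the condition by time ANOVA is the named pre-post analysis. The interaction is its only term that tests whether the arms changed differently. The t-test sentence directly follows the Bonferroni sentence, so it may simply name the test used for those follow-ups. On this view the plan lacks a label, and baseline adjustment is a preference.

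Much of this stands. The interaction is a valid 5% test, and naming it would settle which test decides. It does not say what the t tests cover, and it leaves available precision unused when the correlation is moderate.

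A reader might infer more than the documents support:

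- **That the trial's error rate is nearly doubled.** This needs reading (a) and a willingness to claim on either test. No passage states either. A rate of about 11% would also need the condition main effect to count as a claim, which nothing suggests.
- **That the two tests often conflict.** With true difference 3.2 and change SD 3, they differ on significance in 14% to 63% of simulated trials. This arises only under (a). In 61 of the 63 points at ρ = 0.9 the interaction is significant and the weaker t test is not. Significance in opposite directions occurs in at most 0.03%.
- **That adjustment always narrows the interval.** It does not at ρ of about 0.95 or above, and the documents give no ρ.

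**Conclusion.** The point holds in a limited form. The plan leaves baseline VO2max out of the comparison that answers its aim, and it does not label the deciding test. The interaction is the natural choice and keeps 5%.

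The error inflation, to about 9–10%, is conditional on one of four readings of an ambiguous sentence and on the assumed 19 per arm and ρ of 0.5 to 0.9. It is not an established property of the trial.

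The gain from adjustment depends on ρ. If SD 3 is the change SD, it is about 6 power points and a 12% narrower interval (3.45/3.92 = 0.88) at ρ = 0.5. It is under 1 point and 1% narrower (3.88/3.92 = 0.99) at 0.9, and nil or a trivial loss from about 0.95. At high correlation the main benefit is a fixed rule.

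Separately, if SD 3 is the SD of the analysed variable, a two-sided t test with 38 participants has power 0.89, not the stated 0.95.

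The sections are written in the past tense. A reader might infer that naming a test now would make it prespecified. If data have already been seen, it would not.

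**What to change.** Name one deciding analysis, for example: HIIT and CT will be compared on post-training VO2max in a linear model with arm and baseline VO2max, two-sided alpha 0.05, reported as the between-arm difference with its 95% CI.

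- Report the condition by time interaction as supportive. If adjustment is not adopted, name the interaction as the deciding test.
- State the outcome, time point and scale of the independent t tests. Label them, the condition main effect, VO2 at VAT and maximum VO2/HR as secondary.
- Restate the power in Study Design for the named test, saying whether SD 3 is a change SD or a single-measurement SD and which ρ is assumed.
- If data were seen before the test was named, say so and show the interaction beside the adjusted result.

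**Cost.** No new data are needed, since visits one and two already supply both values. The adjusted model is new to the plan and needs an amendment. It uses one degree of freedom (35 instead of 36 at 19 per arm) and assumes the same linear baseline slope in both arms. The investigators give up any claim based on a test other than the one named.
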